5.6 Data Analysis

Quantitative Statistical Analysis (Aims 1 and 2): Differences in hand hygiene adherence and duration between intervention and control groups will be assessed using Fisher's exact test and t-test, as appropriate. Risk differences in adherence to duration of hand hygiene will be calculated for both intervention and control groups. Because the primary outcomes for Aim 1 (i.e., hand hygiene adherence and duration) are expected to occur frequently, we will use generalized linear models to evaluate differences in hand hygiene adherence and duration for the intervention versus control group, with the Poisson distribution (log link) and robust error variance. Models will account for provider type and level, and will incorporate clustering by physician team (and separately for nursing unit). Statistical significance will be calculated for the intervention (intervention vs. control) coefficient.

As a secondary outcome for Aim 1, we will assess changes and differences in hand hygiene perception based on response to select questions from PSHW. For Aim 2, mindfulness will be based on responses to FFMQ and well-being will be based on responses to WBI. FFMQ and WBI scales will be scored according to the published algorithms. Descriptive statistics will be used to summarize participant scores from pre- and post-intervention, as well as 6-month post-intervention follow-up assessments. Within-group paired-samples t-tests will be used to test for improvement in participant scores across the baseline, post-intervention (~14 days for physicians and 1-month for nurses), and 6-month post-intervention follow-up periods, for the intervention and control groups separately. Analyses will use list-wise deletion for missing data. Participants not completing all surveys will still be included in any analysis for which they provide data. For all analyses, p values less than 0.05 will be considered significant and all tests will be two-tailed. Analysis of covariance (ANCOVA) models will then be used to assess relative changes in mindfulness, well-being, and hand hygiene perceptions across groups, the most direct test of discriminant validity. In these models, post-test scores will be predicted by group status controlling for pre-test scores.

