Mindful Hand Hygiene to
Reduce Infections Among
Veterans While Enhancing
Provider Well-Being

NCT05261282

December 5, 2025

Data Analysis Plan

Differences in hand hygiene adherence and duration between intervention and control groups will be assessed using Fisher's exact test and t-test, as appropriate. Differences in adherence to duration of hand hygiene will be calculated for both intervention and control groups. As a secondary outcome for Aim 1, the investigators will assess changes and differences in hand hygiene perception based on responses to select questions from the PSHW. For Aim 2, mindfulness will be based on responses to the FFMQ and well-being will be based on responses to the WBI. Survey scales will be scored according to the published algorithms. Descriptive statistics will be used to summarize participant scores from baseline and post-intervention, as well as 6-month post-intervention (sustainability) follow-up assessments. Within-group paired-samples t-tests will be used to test for improvement in participant scores across the baseline, post-intervention (~14 days for physicians and 1-month for nurses), and 6-month post-intervention (sustainability) follow-up periods, for the intervention and control groups separately. Participants not completing all surveys will still be included in any analysis for which they provide data. Listwise deletion for observations containing less than 85% complete responses for the FFMQ or WBI items will be used. Missing values for observations with at least 85% responses for the FFMQ or WBI items will be imputed using the average value obtained from non-missing values within each respective subscale. Multilevel linear mixed regression models will be used to assess changes in mindfulness and well-being across groups and the effectiveness of the intervention. Mixed models account for correlation between repeat measurements on the same participant and accommodate missing data across time points. Random effects will be modeled to account for clustering of survey responses at the clinician level. All models will be adjusted for fixed effects for clinician role (physician/nurse) and intervention fidelity. For all analyses, p-values less than 0.05 will be considered significant and all tests will be two-tailed.

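### The SAP does not carry over the protocol's between-arm analysis of hand hygiene perceptions (PSHW), so this Aim 1 secondary outcome has no specified randomised comparison there

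*SAP*

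**What the plan says.** Both documents make hand hygiene perceptions a secondary outcome of Aim 1, but they analyse them differently.

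- Protocol, section 5.6: within-arm paired t-tests come first. Then "Analysis of covariance (ANCOVA) models will then be used to assess relative changes in mindfulness, well-being, and hand hygiene perceptions across groups". The model is written out: "post-test scores will be predicted by group status controlling for pre-test scores".
- SAP, Data Analysis Plan: on perceptions it says that "the investigators will assess changes and differences in hand hygiene perception based on responses to select questions from the PSHW", and names no test or model. The paired t-tests are kept: "Within-group paired-samples t-tests will be used to test for improvement in participant scores across the baseline" and the later periods, "for the intervention and control groups separately". ANCOVA does not appear. The between-arm model is this: "Multilevel linear mixed regression models will be used to assess changes in mindfulness and well-being across groups and the effectiveness of the intervention". Perceptions are not listed in it.
- The SAP's rule for incomplete and imputed survey items names only the FFMQ and WBI.
- The SAP sets two-sided significance at 0.05 for every analysis.

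Neither document says which of the two governs.

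**The concern.** A paired test within one arm asks whether that arm changed. It does not ask whether the arms changed by different amounts, which is the question randomisation was meant to answer. Participants complete the same survey three times, and the protocol's introduction expects the pandemic to keep affecting staff. Some change common to both arms is therefore plausible, from repeated questioning, season or hospital conditions.

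If the SAP is followed as written, the only test that could apply to PSHW is one that counts such shared change as improvement. A significant result in one arm beside a non-significant result in the other would then invite a conclusion about the intervention that the analysis cannot support.

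**Working it through.** **1. The texts side by side.**

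| Outcome | Protocol 5.6, between arms | SAP, between arms |
|---|---|---|
| Mindfulness (FFMQ) | ANCOVA | mixed model |
| Well-being (WBI) | ANCOVA | mixed model |
| Perceptions (PSHW) | ANCOVA | none named |

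The gap is confined to PSHW.

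**2. The plan's own PSHW figure.** The Power paragraph of Protocol 5.6 gives 70.1% power at an effect size of 0.15 and names no test. A two-sided between-arm comparison of means at 0.05 gives a noncentrality of 0.15/√(1/167 + 1/167) = 1.37 and power of 27.8% (28.5% with 167 and 177). A paired test within one arm of 167, with 0.15 in SD of the change score, gives 48.7%. The stated 70.1% appears only with inputs that the documents do not give:
- a paired test at n = 167 with pre-post correlation 0.7;
- ANCOVA with correlation of about 0.83;
- Cohen's f of 0.15 with about 275 completers.

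The figure therefore neither shows which PSHW test was intended nor can be called wrong. The total of 334 in that paragraph, against 344 in section 5.1, does not alter the point.

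**3. Shared change and no intervention effect.** The inputs are n = 167 (intervention) and 177 (control) from Protocol 5.1, and two-sided alpha 0.05 from the SAP. The shared change δ, in SD of the change score, is an assumption and is shown as a range.

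For each arm the paired t statistic has noncentrality δ√n on n − 1 degrees of freedom. Call the probabilities of significance p_I and p_C. The arms are independent, so:
- intervention only = p_I × (1 − p_C);
- control only = p_C × (1 − p_I).

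At δ = 0.15 the noncentralities are 0.15√167 = 1.94 and 0.15√177 = 2.00, so p_I = 0.487 and p_C = 0.510. Intervention only is 0.487 × 0.490 = 0.239. Control only is 0.510 × 0.513 = 0.262.

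| δ | p_I | p_C | Intervention only | Control only |
|---|---|---|---|---|
| 0 | 5.0% | 5.0% | 2.4%* | 2.4%* |
| 0.10 | 25.0% | 26.3% | 18% | 20% |
| 0.15 | 48.7% | 51.0% | 24% | 26% |
| 0.20 | 72.9% | 75.4% | 18% | 20% |
| 0.30 | 97.1% | 97.8% | 2% | 3% |

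*Significant in the direction of improvement. Counting either direction, it is 4.8%.

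**4. The protocol's ANCOVA in the same setting.** Adding the same constant to every post-test score moves the intercept and leaves the arm coefficient unchanged. A simulation of 20,000 trials (assumed pre-post correlation 0.5) agrees: the ANCOVA arm term is significant in 5.1%, 5.0% and 5.1% of trials at δ = 0, 0.15 and 0.30.

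Steps 3 and 4 assume no attrition, no clustering by team or unit, and one continuous PSHW score. The documents describe eight selected questions and state no composite.

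**The case against.** The strongest reply is that the documents taken together do contain a between-arm test for PSHW. Protocol 5.6 specifies it, and nothing says that the one-paragraph SAP supersedes it. The SAP's mention of changes and differences may itself intend a comparison of arms. The paired-test sentence speaks of participant scores and follows the text on scoring the survey scales, so PSHW may have no named test in the SAP at all. All of this stands. It makes the finding a disagreement between documents and an omission in the SAP, and it does not remove the omission.

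Three stronger readings are tempting and are not supported.

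- *That FFMQ and WBI will also be judged by within-arm tests.* The SAP assigns the effectiveness of the intervention to the mixed model across groups. It does not write out an arm-by-time term or say which result decides, but nothing says that significance in one arm only will count as an effect.
- *That the paired tests favour the intervention.* Control-only significance is slightly more likely at each non-zero shared change shown. The 24% at 0.15 SD is close to the maximum, because each test then has about 50% power. The pattern is rare when shared change is absent or large. The exposure is misleading noise, or a misleading result if the intervention arm is read alone.
- *That 3 scales × 3 time pairs × 2 arms = 18 tests carry a 60% chance of a false positive (1 − 0.95^18).* This needs independent tests, yet the third time contrast is determined by the other two. It also needs every null to hold, which excludes the shared change at issue. Twelve of the 18 tests concern scales that already have a between-arm model.

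**Conclusion.** The point holds for PSHW. Followed as written, the SAP gives a named secondary outcome of Aim 1 no specified randomised comparison, although the protocol has one. If the paired tests are what is applied, modest shared change can mislead. At 0.10 to 0.20 SD of the change score, the intervention-arm test alone is significant in 25% to 73% of trials with no intervention effect. The intervention-only pattern occurs in 18% to 24%, against about 5% for a between-arm ANCOVA. The size of any shared change is assumed and does not come from the documents. The rates also rest on full follow-up, independent participants and a single PSHW score.

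For FFMQ and WBI the point is a clarification only. A reader might infer that the trial has no between-arm test of perceptions anywhere, but Protocol 5.6 rules that out. The matter is worth settling before the analysis, and it affects one secondary outcome, not the primary ones.

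**What to change.** Reconcile the two documents in the SAP.

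- **Restore the between-arm analysis of PSHW.** Use the protocol's model (post-test on arm, adjusted for pre-test) or a mixed model with an arm-by-time term. Say whether the eight questions are analysed singly or as a score, and which missing-data rule applies.
- **Leave intervention fidelity out of this model.** The SAP adjusts all models for fidelity, but Protocol 5.1 and 5.5 build it from module completion, app use and discussion attendance. These arise after randomisation and only in the intervention arm, so adjusting for them would distort the arm contrast.
- **Account for clustering by physician team and nursing unit**, the units that are randomised. The SAP's random effects are at clinician level only.
- **State which result decides.** The intervention effect on PSHW, FFMQ and WBI is judged by the arm contrast, and within-arm changes are descriptive.

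The cost is about two SAP sentences and a little more analysis. No new data are needed.

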5.0 Study Procedures

5.1 Study Design

Research Design: A multi-center, repeat-measures randomized controlled mixed-methods trial.

Study Population: The proposed study will focus on Internal Medicine physicians who are part of inpatient care teams and nurses providing care on medical and medical/surgical units at LTC Charles S. Kettles VAMC in Ann Arbor, MI and MEDVAMC in Houston, TX. Medical students, surgical physicians, and physicians on sub-specialty teams will not be included. At both participating facilities the inpatient care teams are predominately composed of 1 attending, 1 senior resident, 2 interns, and up to 3 medical or physician assistant students. Interns and senior residents are usually assigned to a team for 4-week blocks (occasionally 2 weeks), while attendings rotate approximately every 2 weeks. The Ann Arbor VAMC has 3 medical or medical/surgical inpatient units, while MEDVAMC has 5 units. At both facilities each nursing unit employs between 20-30 nurses. We will aim to recruit approximately 30 attendings, 72 residents and 40 nurses at Ann Arbor VAMC. As MEDVAMC is larger, with a greater number of inpatient care teams and nursing units than the Ann Arbor VAMC, we will aim to recruit approximately 40 attendings, 72 residents and 90 nurses. Our target study sample size is a total of 344 physicians and nurses (167 intervention/177 control). For Aim 3, we plan to interview approximately 8 physician team members and 4-6 nurses from the intervention arm at each site.

General Study Overview and Outcome Measures:

A summary of the proposed study activities at each participating site is presented in **Table 2** below.

Table 2: Overview of Study Activities at Each Study Site

| Study Detail | Physicians | Nurses |
|----------------------------------|--|--|
| Target | Attendings, senior residents and interns on inpatient medicine teams | Nurses on medical or medical/surgical units |
| Teams/Units Participating | 2 teams each month for 12 months randomized to intervention or control arm at each site | 2 units (1 intervention; 1 control) at Ann Arbor VAMC & 4 units (2 intervention; 2 control) at MEDVAMC randomized once & followed for 12-months |
| Estimated number of participants | 107 intervention and 107 control | 20 intervention and 20 control at Ann Arbor VAMC; 40 intervention and 50 control at MEDVAMC |
| Habituation Period | 1 month | 1 month |

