Pre-Intervention Assessment - To evaluate mindfulness and hand hygiene, inpatient medicine teams and nurses from medical and medical/surgical units at each participating hospital will be included. Following informed consent, physicians from selected teams and nurses from selected units will be asked to complete a survey containing validated scales measuring dispositional mindfulness, well-being, and hand hygiene perceptions (**Appendix B**). The Five Facet Mindfulness Questionnaire (FFMQ)⁷⁵ is a validated instrument with favorable psychometric properties and consists of 39 questions. Additionally, participants will be asked to complete the Well-Being Index (WBI). The 9-question WBI assesses distress across a variety of dimensions including fatigue, depression, burnout, stress, and quality of life, and has been validated for use in physicians,⁷⁶ residents,⁷⁷ and nurses.⁷⁸ Participants will also be asked to complete 8 questions on HAI and hand hygiene perceptions selected from the Perceptions Survey for Healthcare Workers (PSHW) developed by the World Health Organization.⁷⁹ Similar to other studies on hand hygiene perceptions guided by the constructs based on the Theory of Planned Behavior,⁸⁻¹⁰ the selected PSHW questions cover behavioral, normative, and control beliefs, as well as self-reported hand hygiene adherence. Participants will also be asked whether they meditate or perform any form of internal reflection prior to the study, as this may influence performance during the intervention. Questionnaire completion will take approximately 10 minutes. When feasible, surveys will be distributed in person with a postage-paid return envelope. Each survey will be labeled with a unique study ID number to allow us to track response. When we are unable to distribute the surveys in person – for example, when a physician rotates to another facility during residency – the surveys will be distributed using an electronic survey tool such as Qualtrics or RedCap. As physicians will need to access the survey's from outside the VA firewall (if they have rotated to another facility), we will use programs hosted by the University of Michigan. The informed consent document will include that survey data may be collected outside the VA firewall, however no personal identifiable information will be collected with the surveys to protect confidentiality. Subjects will always have the choice to complete the survey on paper if they would prefer.

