Power - Based on a range of 10%-15% significant percent change in hand hygiene adherence from our pilot data,⁷² we are anticipating an expected increase in hand hygiene adherence due to the intervention from approximately 80% at baseline to 88%-92% at follow-up. We will have 79.8% power to detect this 10% increase based on a fixed total sample size of 334 with a two-sided alpha of 0.05, assuming an average of 60 observed hand hygiene opportunities per provider per measurement time point (i.e., intervention and follow-up), and taking into account clustering of data within site/team/unit (assumed Intraclass Correlation Coefficient=0.4).⁸² For assessing differences in the select PSHW questions we will have 70.1% power to detect an effect size of 0.15.⁸³ For assessing differences in FFMQ and WBI scores, we will have >95% power to detect effect sizes ranging from 0.3 to 0.75 as found in prior studies.^{65,84,85}

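### The SAP's mixed model for FFMQ and WBI does not carry over the protocol's pre-test adjustment or say how baseline enters, and no analysis uses prior meditation

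*SAP*

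**What the plan says.** Protocol section 5.6 names ANCOVA as the between-arm analysis for mindfulness, well-being and hand hygiene perceptions: "post-test scores will be predicted by group status controlling for pre-test scores". The same paragraph sets list-wise deletion, but also keeps people with incomplete surveys in whatever analyses their data allow.

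The SAP (Data Analysis Plan) does not mention ANCOVA. For FFMQ and WBI it says: "Multilevel linear mixed regression models will be used to assess changes in mindfulness and well-being across groups and the effectiveness of the intervention". Its reasons are that such a model handles within-person correlation and missed surveys. It places random effects at clinician level and lists two adjustment terms for all models: clinician role and intervention fidelity. It does not set out arm, time or arm-by-time terms. It does not say whether the baseline score is an outcome or a covariate, or whether baseline means may differ by arm. Because it speaks of changes and of repeated measurements over three surveys, the likeliest reading is that baseline is the first outcome.

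In protocol section 5.1 (Pre-Intervention Assessment), and again in 5.5, participants are to be "asked whether they meditate or perform any form of internal reflection prior to the study, as this may influence performance during the intervention". Neither protocol section 5.6 nor the SAP uses the answer.

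**The concern.** How the baseline score enters the model decides how much of its information reaches the arm contrast. The protocol made that choice and the SAP reopened it. A natural reading of the SAP is a model with free means for each arm at each survey, baseline included. With complete data that model returns the difference in mean change, which is less efficient than baseline adjustment. Two analysts could both follow the SAP and report different intervals, and the choice could be made after the results are seen.

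Prior meditation matters because of how this trial recruits. There are three nursing units per arm, and nurses are approached after allocation by routes that differ by arm. Nurses on intervention units give written consent to a mindfulness programme, while those on control units consent by returning a survey (protocol sections 5.2 and 5.3). People who already meditate could therefore enter the arms at different rates. The one variable that measures this is collected and then left unused.

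**Working it through.** **Inputs**

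- Test level, from the SAP: "For all analyses, p-values less than 0.05 will be considered significant and all tests will be two-tailed".
- Arm sizes: 167 and 177, the target of 344 in protocol section 5.1. The power paragraph in 5.6 is instead "based on a fixed total sample size of 334 with a two-sided alpha of 0.05", which is 167 per arm if split equally.
- Stated power, protocol section 5.6: "For assessing differences in FFMQ and WBI scores, we will have >95% power to detect effect sizes ranging from 0.3 to 0.75". The test, the type of effect size and the correlation are not given.
- Correlation r between baseline and follow-up: not in the documents, so assumed, over 0.3 to 0.9.
- Simplifications: score SD of 1 at every survey, independent individuals, complete data (until step 3), and role and fidelity terms left out.

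**Step 1: the plan's own figure.** Ignoring baseline, power at d = 0.3 is Φ(0.3/SE − 1.96) with SE = √(1/n₁ + 1/n₂).

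- 167/167: SE = 0.1094, power 78.3%.
- 177/167: SE = 0.1079, power 79.4%.

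Neither exceeds 95%. A paired within-arm test at d = 0.3 does: 97.1% with n = 167 and 97.8% with n = 177. With 167 per arm, a between-arm test reaches 95% only if r is about 0.65 or more (ANCOVA) or about 0.71 or more (change). With no r stated, the figure can be neither confirmed nor refuted as a between-arm claim.

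**Step 2: cost of free baseline means.** Let f = 1/177 + 1/167 = 0.01164.

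- Variance of the change contrast: 2(1 − r)f
- Variance of the baseline-adjusted contrast: (1 − r²)f
- Ratio of interval widths: √[2(1 − r)/(1 − r²)] = √[2/(1 + r)]

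Generalised least squares for a three-survey model with equal correlations agrees with these formulas:

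| r | SE, ANCOVA | SE, mixed model, free baseline means | SE, mixed model, equal baseline means | Width, free ÷ ANCOVA | Power at d = 0.3, ANCOVA | Power at d = 0.3, free |
|---|---|---|---|---|---|---|
| 0.3 | 0.103 | 0.128 | 0.103 | 1.24 | 0.830 | 0.652 |
| 0.5 | 0.093 | 0.108 | 0.093 | 1.15 | 0.895 | 0.794 |
| 0.7 | 0.077 | 0.084 | 0.077 | 1.08 | 0.973 | 0.949 |
| 0.8 | 0.065 | 0.068 | 0.065 | 1.05 | 0.996 | 0.993 |
| 0.9 | 0.047 | 0.048 | 0.047 | 1.03 | 1.000 | 1.000 |

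At r = 0.7 the choice decides on which side of the stated 95% the analysis falls.

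**Step 3: missing surveys.** Assumed pattern: 60% complete all three surveys, 15% baseline and post-intervention, 10% baseline and 6 months, 10% baseline only, 5% both follow-ups without baseline. Width of the free-baseline mixed model relative to ANCOVA:

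| r | 0.3 | 0.5 | 0.7 | 0.8 | 0.9 |
|---|---|---|---|---|---|
| ANCOVA on the 75% with baseline and post-intervention | 1.17 | 1.10 | 1.05 | 1.02 | 1.00 |
| ANCOVA on the 60% with all three | 1.05 | 0.99 | 0.94 | 0.91 | 0.89 |

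**Step 4: prior meditation.** If it explains a share R² of the variance left after baseline, omitting it widens the interval by 1/√(1 − R²). For assumed R² of 0.01, 0.05 and 0.10 this is 0.5%, 2.6% and 5.4%.

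**The case against.** A reader might infer from the missing covariate that the Aim 2 intervals are wider, or that the SAP model is always less precise than the protocol's. The documents support neither. The SAP does not say that baseline means are free, and if they are constrained equal the loss is zero. The SAP chose the mixed model partly to cope with missed surveys, and many residents rotate away before follow-up (protocol section 5.1, Aim 2 risks). Step 3 shows that even the free-baseline version can be narrower than ANCOVA on people with all three surveys. This objection stands, and it makes the size conditional.

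It is also tempting to read the variance ratio (1 + r)/2, which is 0.75 to 0.85 at r = 0.5 to 0.7, as equivalent to discarding 15 to 25% of participants. That does not carry over. Teams and units are what is allocated, the ratio then depends on cluster-level correlation too, and losing participants alters only the within-cluster part of the variance.

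The correlation may be high: the protocol calls the FFMQ construct dispositional, and the first retest comes at about 14 days or 1 month. At r of 0.8 to 0.9 the excess is only 3 to 5%. That is plausible but undocumented.

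On prior meditation, a stable difference in score level cancels out of a change contrast, so only an effect on change would remain. The protocol's remark does not commit to adjustment, and its own ANCOVA did not include the item. The precision gain is therefore unknown and probably modest. The case for the item rests on possible imbalance from recruitment, which adjustment would reduce but not wholly remove.

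Finally, recruitment after cluster allocation means that equal baseline means are not guaranteed by design. This stands and limits the choice of fix.

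**Conclusion.** The point holds as an adjustment not carried over and a model left under-specified. The protocol fixed the pre-test score as a covariate. The SAP replaces that analysis, names only role and fidelity, and does not say how baseline enters. If baseline means are left free by arm, intervals are about 15% to 8% wider than baseline-adjusted ones at r = 0.5 to 0.7, with 24% at 0.3 and 3% at 0.9 as the outer values. These figures rest on an assumed correlation, equal variances over time, complete data and independent individuals; clustering by team and unit would change them. They are not a statement that the trial's intervals will be wider.

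It also holds that prior meditation is collected for a stated reason and then used in no analysis. The size of any benefit from using it cannot be derived from the documents.

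Intervention fidelity, which is measured after allocation and sits in the same covariate list, raises a separate question about what the arm effect means. It is not settled here.

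**What to change.** Keep the mixed model and specify it in the SAP:

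1. Outcomes: the post-intervention and 6-month scores. The pre-test score is a covariate, as in the protocol.
2. Fixed effects for arm, time and arm by time. Take the effect at each follow-up from the arm-by-time contrast.
3. Prior meditation (yes/no) as a fixed effect.
4. A stated rule for people without a baseline score, for example mean imputation of the baseline covariate. This is the one small drawback against treating baseline as an outcome.
5. The model with baseline as an outcome and equal means across arms as a sensitivity analysis only, because recruitment follows cluster allocation and nurse consent differs by arm.

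The cost is a few sentences of SAP text and a few lines of code. Both baseline values are already collected, and the mixed model's use of people who miss one follow-up is kept.
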